Our team is comprised of highly experienced adolescent HIV prevention researchers, including [name] and [name], who have a long history of research that seeks to address the key health issues facing South African adolescent girls while at the same time protecting this vulnerable population. The research sites have considerable experience in conducting clinical research in adolescent populations.

Figure 2. HIV incidence (%) by age and sex in South Africa

[figure not shown]
[figure not shown]

Figure 3. Adolescent pregnancy in South Africa, 2010-2013

Our study, PrEP-PP (PrEP in Pregnant and Postpartum women) will determine the distribution of women across the PrEP cascade (i.e. PrEP initiation, retention, and adherence) in a cohort of HIV- pregnant and breastfeeding adolescent girls and women in two public health facilities in South Africa to inform policymakers about the efficacy of PrEP integration into antenatal (ANC) and postnatal care in high HIV incidence communities.

2. Study objectives:

The objectives of the study are to:

1. Determine the distribution of women across the PrEP cascade:
 - (1) Evaluate the proportion of pregnant and breastfeeding women who initiate PrEP out of all women offered PrEP
 - (2) Evaluate the proportion of pregnant and breastfeeding women who are retained in the PrEP cohort
 - (3) Evaluate the proportion of pregnant and breastfeeding women who initiate PrEP who adhere to PrEP using objective dried blood spot measures and subjective measures of self-reported pill count and adherence
 - (4) Evaluate the proportion of pregnant and breastfeeding women on PrEP (and not on PrEP) who acquire HIV, who transmit HIV to their infant, and who report adverse events
2. Evaluate patient and provider-level factors associated with the PrEP cascade using quantitative and qualitative approaches (including in-depth interviews)

3. Study design

To address these objectives, we will conduct an observational cohort study in 220 pregnant women who will be recruited at the first antenatal care (ANC) visit from the Gugulethu Midwife Obstetric Units in Cape Town. We will follow the enrolled women through 12-months post-delivery.

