Step 11: Participants will receive counselling on the risks and benefits of PrEP. Following the counseling they will be asked: “Do you want to start taking PrEP today to prevent HIV? You will need to take it daily for it to be effective.” Her response will be recorded.

If yes:

1. The nurse will provide the participant with a 1-month supply of TDF-FTC and invite her to return in 1 month for her next study visit.
2. Nurses will provide contact information to the participant and ask her to call to report any side effects or adverse events while on PrEP, and nurse will track and report serious adverse events to study PIs, Pediatrician, and Obstetrician to decide on how to treat women and infants who have adverse events.

If she says she does not want to start PrEP, woman will be in the deferred PrEP arm:

1. The nurse will schedule her to return in 1 month for the follow-up visit

Step 12: Participants will receive study staff contact information, instructions to call with any questions, and will be scheduled for their next visit in 1 month for the next study visit

Step 13: Participants will receive study staff contact information, instructions to call with any questions, and will be scheduled for their next visit in 1-week to return when test results have returned from the laboratory

Step 14: The study counselor will provide the mother with an appointment card and invitation for her partner to return to receive couples’ HIV testing and counseling (if in a relationship). The session will end by encouraging the client to implement her/his risk-reduction plan (including PrEP if applicable and consistent condom use, couples testing) to prevent HIV acquisition.

Step 15: The participant will receive up to R250 per visit including reimbursement for the participant’s time, transportation and including their refreshments during the study. Further, we will combine the study visits with existing ANC or post-partum/well-baby visits to minimize the travel to the facilities outside of normal clinical checkups.

2. For follow up return visits:

Follow up visits will be monthly until birth (to coincide with ANC visits) then every two months after birth (to coincide with post-partum, well-baby visits).

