Step 1: In ANC: Healthcare providers provide counseling on HIV prevention and treatment at each ANC visit including HIV testing, as part of standard of care. In post-natal care and well-baby visits women may not receive regular HIV testing and messages and will receive this within step 2 (with study counselor). Following their ANC visit, enrolled women will be invited to attend the study site in each MOU to do the follow-up visit including the ACASI survey and prescription and adherence counseling (if on PrEP).

Step 2: ACASI survey at each visit in a private study room

Step 3: In the study room, the study counselors will provide PrEP-specific counseling including adherence counseling for those on PrEP (and management of side effects), or counseling about the risks and benefits of PrEP for women not yet on PrEP. Women not on PrEP will be asked if they are interested in starting PrEP at this visit.

Step 4: STI testing: At 3rd trimester visit and first postpartum visit, participants self-collect a vaginal swab for STI testing (chlamydia, gonorrhea and trichomonas vaginalis using Cepheid® point of care testing). Participants will be treated if diagnosed with a STI according to National Guidelines. They will receive a partner notification letter to bring their partner in for treatment as well.

Step 5 (for women on PrEP): At each visit the study counselor will ask, and record responses, all participants on PrEP about any side effects associated with TDF/FTC, including diarrhea, nausea, fatigue, headache and rash (which are seen in about 10% of participants during the initiation of therapy). We will encourage participants to contact the study nurse if they experience side effects between visits.

For participants on PrEP, the study nurse performs a blood draw for creatinine clearance and a finger prick for DBS testing for adherence measures and (if applicable for this visit). See Table 1 for study calendar.

Step 6: PrEP provision (for 1 or 2 months) and appointment reminder

Follow-up & retention: Tracing information will be taken at the enrolment visit and updated at each study visit. Retention activities will focus on scheduled measurement visits. Following our established approach in this setting, we will provide reminder calls to participants before their measurement visits, and initiate tracing, including home visits, for women who do not attend the measurement visit within one week of the scheduled visit.

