 - If a woman seroconverts while on PrEP, there may be a risk of ART resistance, though research has demonstrated that the risk of ART resistance is very low [12, 13]. In the case of seroconversion, Drs [name] and [name] will follow seroconverters with the study team to evaluate if the patient achieves viral suppression within 6 months of ART start, and if not, she will be referred for specialist attention for testing for ART resistance and clinical follow-up.

Adverse events:

- **Maternal adverse events:** We will collect data on maternal adverse events by asking mothers about intercurrent medical events, which will be reviewed by an obstetrician, including any hospitalizations or illnesses. We will also track and report changes in creatinine or other toxicities in women on PrEP.
- **Infant adverse events:** We will collect data on infant adverse events by asking mothers about infant health or intercurrent medical events, which will be reviewed by a pediatrician.
 - Adverse birth outcomes will include infants that were small for gestational age, pre-term births, miscarriage and stillbirths.

Table 1: PrEP-PP cohort measures by participant study month

Participant study month	Pregnancy						Post-partum											
	1	2	3	4	5	6	7	8	9	10	11	12	13	14	15	16	17	18
Study enrollment and consent of consecutive sample of HIV-negative pregnant women (N=220)	X																	
PrEP group, individual (or couples counseling where applicable) and information, education, counseling materials on PrEP in pregnancy and breastfeeding in local languages (at each visit)	X	X	X	X	X	X	X		X		X		X		X			X
Routine ANC and postnatal care, well-baby visit follow-up (as available in standard of care), including rapid HIV testing, pregnancy, and birth outcomes	X	X	X	X	X	X	X		X		X		X		X			X
ACASI survey to collect: behavioral acceptability, knowledge, and substance use data	X	X	X	X	X	X	X		X		X		X		X			X
Screening at enrolment for Hepatitis B surface antigen. If HBsAg+ = excluded from study	X																	
Laboratory testing for STIs (chlamydia and gonorrhoea) & treatment if positive	X				X		X											
For women on PrEP:																		
Laboratory tests of creatinine (if eGFR<60ml/min cannot continue on PrEP, refer to return in 1 month for re-test)	X			X			X								X			X
PrEP pharmacy refills and adherence supportive counseling monthly (for first 3 months on PrEP) then every 2 months for following months	X	X	X		X		X		X		X		X		X			X

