There are four sources of data/materials for this trial: (1) survey measures (ACASI); (2) in-depth interview measures in 20 randomly selected women (n=10 who were on PrEP compared with 10 not on PrEP); (3) laboratory measures; and (4) information abstracted from routine care records, including related to PrEP. The collection of data materials will be conducted by a study measurement team comprised of one study coordinator, one study interviewer, and one fieldworker. All procedures for data collection (regardless of source) will be outlined in a study manual of procedures, with individual activities guided by standard operating procedures (e.g., DBS, specimen transport, or questionnaire administration).

Survey measures (ACASI)

At study measurement visits, questionnaires will be administered to mothers participating in the study using ACASI on a tablet with a site coordinator available for troubleshooting. ACASI will help reduce the amount of respondent bias when responding to sensitive questions around sex and substance use. Following standard procedures, the questionnaires will be translated into isiXhosa and Afrikaans and back translated to ensure appropriate phrasing. Questionnaires will include:

- Basic demographic information and obstetric history (enrollment only)
- Partner's HIV status
- Sexual behaviors in the past month and week including # of sex partners, type of sex, and frequency of sex and condom use
- Substance use information using the AUDIT-C and DAUDIT scales
- Risk perception scales
- Partner, community and social support for PrEP
- For PrEP users, questions related to PrEP adherence according to self-report (the 3-day and 1-month recall and a visual analog scale) and pharmacy-based pill counts will be conducted at each study measurement visit.
- Additional schedules will be used to collect data on symptoms in mothers that are potential side-effects of PrEP use (at all study visits)
- We will also use short questionnaires to collect data on all women's experiences in the study, and the acceptability of the PrEP initiation, including what kind of services were offered at each visit (e.g. counseling, peer mentorship, and IEC materials, medication)
- Self-reported symptoms related to STIs

- This will focus on the positive and negative aspects of their experiences of PrEP initiation in pregnancy and breastfeeding and any factors associated with PrEP initiation, retention, and adherence.

Interview measures

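### Side effects are actively elicited by staff only from women on PrEP, and Table 2 takes them from the provider log, so on/off-PrEP adverse-event reporting may show a spurious excess on PrEP unless a symmetric source is named

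*Combined protocol and SAP*

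**What the plan says.** All references are to the combined protocol and SAP.

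**Routes limited to women on PrEP**
- Section 5, follow-up visits: "Step 5 (for women on PrEP): At each visit the study counselor will ask, and record responses". The question goes to "all participants on PrEP about any side effects associated with TDF/FTC", with diarrhoea, nausea, fatigue, headache and rash named.
- Section 5, enrolment Step 11, in the branch for women who accept PrEP: nurses give contact details and "ask her to call to report any side effects or adverse events while on PrEP". The branch for women who defer contains only the next appointment.
- Section 5, Adverse events: "We will also track and report changes in creatinine or other toxicities in women on PrEP".

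**Routes with no stated restriction**
- Sources of data, Survey measures (ACASI): "Additional schedules will be used to collect data on symptoms in mothers that are potential side-effects of PrEP use (at all study visits". A neighbouring item in the same list is explicitly limited: "For PrEP users, questions related to PrEP adherence according to self-report". The symptom item carries no such label.
- Section 5, Adverse events: mothers are asked about intercurrent medical events, including illness and hospitalization, with review by an obstetrician.

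**Reporting**
- Section 2, Objective 1(4) covers "women on PrEP (and not on PrEP) who acquire HIV, who transmit HIV to their infant, and who report adverse events".
- Section 6, Table 2 gives the electronic provider log as the source for side effects and other health outcomes. ACASI is named in that table only for predictors of attrition.
- Section 6 describes side effects by counts and person-time, with confidence intervals for the latter. No test of symptoms on versus off PrEP is specified.

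**The concern.** Nausea, fatigue and headache are ordinary complaints of pregnancy. A woman who is read a list of symptoms at every visit, and told to call about them in between, will have more of them recorded than a woman who is not. When exposure decides who is prompted, a difference in recorded symptoms mixes any drug effect with the difference in questioning.

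The objective places the two groups side by side. Even without a formal test, two proportions or two rates with confidence intervals will be read as a comparison. The background section says that adverse drug effects in HIV-uninfected women need further evaluation, and the study is meant to inform policymakers. A false excess on PrEP would count against its use in this group.

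The plan allows women to stop and restart PrEP. A woman who stops also leaves the Step 5 questioning, so ascertainment changes within a woman at the moment her exposure changes. Analysis cannot repair this afterwards if the symptoms were never asked about in the same way.

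**Working it through.** The documents contain no figure to reproduce. The check is a comparison of the collection routes, followed by arithmetic on assumed capture rates.

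**1. Routes side by side**

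| Route | On PrEP | Not on PrEP | Names the symptoms? |
|---|---|---|---|
| Counsellor question, follow-up Step 5 | Yes, each visit | No | Yes |
| Prompt to call between visits, enrolment Step 11 | Yes | No | No, general |
| ACASI symptom schedule | Yes | Apparently yes | Refers to potential PrEP side effects |
| Maternal adverse-event questions | Yes | Yes | No, intercurrent events |

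Table 2 points to the provider log. Step 5 is the only procedure in which staff are explicitly told to ask about the named symptoms. Following Table 2 literally therefore takes these symptoms from the unequal route. The plan never says which source serves the on/off report.

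**2. Bias with no true effect**

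Let p be the true risk of a symptom, equal in both groups. Let s1 be the share captured on PrEP and s0 the share captured off PrEP.

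Apparent risk ratio = (p × s1) / (p × s0) = s1 / s0.

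Assumed values, not in the documents: s1 = 0.9; s0 = 0.5 to 0.7.
- 0.9 / 0.7 = 1.29
- 0.9 / 0.5 = 1.80

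This applies to risk per visit or to episode rates. A proportion of women ever reporting a symptom over many visits would be distorted less on the ratio scale, because repeated episodes give further chances of capture.

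**3. Pooling does not remove it**

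Suppose ACASI captures a share a in both groups, and the counsellor route picks up a share k of what ACASI missed, in PrEP users only.

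Apparent ratio = [a + (1 − a) × k] / a.
- a = 0.7, k = 2/3: (0.7 + 0.2) / 0.7 = 1.29
- a = 0.5, k = 0.8: (0.5 + 0.4) / 0.5 = 1.80

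So the same range arises when both sources are combined. With ACASI alone, k = 0 and the ratio is 1.00.

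**4. Would a cohort of 220 show it?**

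Illustration only, since the plan specifies no test. Set capture at 100% on PrEP and 50% off PrEP, so the ratio is 2.00. Uptake of 50%, 70% or 90% is assumed. The 30% symptom risk is assumed; 10% is the protocol's own figure for side effects at initiation.

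Chance of a nominal two-sided 5% result = Φ[(d − 1.96 × SE0) / SE1], with d the difference in recorded proportions, SE0 the pooled and SE1 the unpooled standard error. For 110 versus 110, with 0.30 versus 0.15 recorded:
- d = 0.15
- SE0 = √(0.225 × 0.775 × 2/110) = 0.0563
- SE1 = √[(0.21 + 0.1275)/110] = 0.0554
- Φ[(0.15 − 0.1104)/0.0554] = 0.76

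| On / off PrEP | True risk 30%, spurious difference 15 points | True risk 10%, spurious difference 5 points |
|---|---|---|
| 110 / 110 | 0.76 | 0.29 |
| 154 / 66 | 0.66 | 0.20 |
| 198 / 22 | 0.28 | 0.06 |

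The artefact could be conspicuous for common symptoms at moderate uptake. It would probably pass unnoticed for rarer symptoms or when nearly all women take PrEP.

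**The case against.** **The ACASI schedule already covers all women.** The symptom item speaks of mothers, applies at all visits, and lacks the users-only label that the adherence item carries. Table 1 places ACASI above its block for women on PrEP. This is the natural reading and it largely stands, so it cannot be said that women off PrEP go unasked. It does not settle the matter. The wording could still be read as users only, the Table 1 row for ACASI does not list symptoms, and Table 2 names another source.

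**Table 2 may simply be loose.** It also credits the provider log with self-reported adherence, which the ACASI list collects. That is fair, and it makes this a matter of clarification. As written, though, the named source is the unequal one.

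**Objective 1(4) concerns adverse events, not drug side effects, and those questions go to all mothers.** This stands for illness and hospitalization. Those questions do not name nausea, fatigue or headache, and Table 2 puts side effects and adverse events in one row.

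**Step 5 is ordinary safety monitoring, and every participant gets contact details.** Both are true. Step 5 need not change. The general invitation to call is for questions, whereas PrEP starters are specifically asked to report symptoms.

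**A stronger reading is tempting:** that the study will make PrEP appear to cause pregnancy symptoms. The documents do not support it. A symmetric source appears to exist, the analysis is descriptive, the study is described as a pilot, and no passage commits the analysts to the counsellor data for an on/off contrast. The creatinine sentence adds nothing here either: creatinine is a laboratory value, and Section 5 and Table 1 differ on whether all women are tested.

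**Conclusion.** The point holds as a gap in the plan: staff elicitation is unequal, Table 2 names the provider log for side effects, and the source for on/off reporting is not stated. A spurious excess on PrEP may follow if the log is used alone or pooled with ACASI. It does not follow if only an identically administered ACASI schedule is used.

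The size cannot be known from the documents. The range of 1.3 to 1.8 rests wholly on the assumed capture of 90% against 50% to 70%, on equal true risks, and on per-visit or per-episode reporting. It shows the mechanism and is not an estimate for this study. The change is worth making because it is cheap and must precede data collection.

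**What to change.** 1. In Survey measures (ACASI), state that the symptom items go to all women at every study visit, whatever their PrEP status, in identical wording that does not presuppose PrEP use.
2. In Table 2, make this schedule the sole source for symptom reporting on versus off PrEP, with PrEP status updated at each visit.
3. Use the unrestricted maternal adverse-event questions for other events in both groups, and confirm that they are put to women not on PrEP.
4. Report Step 5 and call-in data descriptively, within PrEP users only and without a comparator. Their use in care stays as it is.

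The cost is a few sentences, an edited table row and at most about a minute of extra survey time, or none if the items already go to everyone. Two limits remain and should be stated with the results: women choose whether to take PrEP, and counselling about its side effects may make users readier to report symptoms even on an identical questionnaire.

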- **DBS:** Dried blood spots will be prepared from finger pricks every two months in women on PrEP to evaluate adherence.
 - DBS cards will be prepared and stored following standard protocols and stored at -80°C for analysis at the end of the study with the clinical pharmacodynamic laboratory of [name] at UCT. Using techniques developed by [name] at University of Colorado [16] adherence will be defined as red blood cells containing TDF-DP ≥ 40 ng/dl which is indicative of daily dosing [16]. As supplementary measures of PrEP adherence, we will use self-reported items that we will adapt from previous studies (including visual analogue scales as well as 3-day, 30-day and last visit recall questionnaires) (22-25), and pharmacy refill records to compare objective versus subjective measures and report on the effectiveness of each measure in correlation to the true measures of TDF-DP. We will determine final dosing and measures following reporting from ongoing PK studies of pregnant women on PrEP (e.g. Impaact 2009).

Laboratory tests in all women in the cohort:

- **STI testing (baseline, 3rd trimester and first postpartum visit):** Self-collected vaginal swab kits will be provided to all participants along with an explanation for their use. Swabs will be analyzed using on-site testing equipment (GeneXpert; Cepheid ®) for rapid testing of chlamydia, gonorrhoea and trichomonas vaginalis. If they test positive, they will be treated by the nurse/midwife in ANC or postpartum care and a referral for her partner to receive STI treatment in the clinic.
- **HIV testing.** As part of the standard of care, all pregnant and breastfeeding women will be tested for HIV using serial rapid HIV tests at each antenatal and postnatal care visit. In addition, PrEP-PP study staff will have a stock of rapid HIV test kits to ensure that women get tested at each study visit.
 - **Seroconversion.** If a woman, infant or partner seroconverts at any point during the study, they will be referred to the clinician on duty to initiate ART, following counseling about PMTCT, breastfeeding, disclosure, and ART adherence, per the SA National Protocols [17]. Seroconverted women will be censored from the remainder of the study and referred to the clinic to initiate ART.

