The primary analysis will focus on measuring the distribution of women across the PrEP cascade including: initiation, retention and adherence. **PrEP initiation** will be based on a woman’s uptake of PrEP and allow for stoppage and re-initiation; **PrEP retention** will be defined as not missing >1 visit among those on PrEP (with separate analyses of PrEP stoppage). For **PrEP adherence** for women on PrEP we will measure both **perfect adherence** (i.e. level of objective adherence throughout pregnancy and breastfeeding periods) as well as “**prevention-effective**” adherence (i.e. adherence before and during times of sexual activity) in participants through objective and subjective measures to evaluate agreement between the two measures, and the level of under- or over-reporting. Primary adherence analyses will use objective measures (TDF-DP from DBS) taken on all those who enrolled and initiated PrEP; subsidiary analyses will consider (i) other adherence measures and (ii) multiple imputation for missing adherence data.

- **Use of PrEP will be measured** through alternate definitions of the main outcomes (e.g. adherence by self-report versus adherence by pharmacy refill), compared using measures of agreement and will be analyzed as independent models to contrast estimated associations.

- **Measurement of prevention-effective execution:** Execution refers to PrEP adherence during a time when at-risk sex happens. It is calculated by: number of doses reported, or recorded/number of expected doses based on HIV risk and PrEP initiation/discontinuation
- **Prevention-effective continuation:** Prevention-effective continuation describes the duration of PrEP use during periods of HIV risk and references the absolute time of use during pregnancy and breastfeeding periods. We will adapt the methodology from previous PrEP studies in SA including FEM-PrEP to create a semi-ordinal composite adherence score from blood specimens from DBS every 2-months.

Table 2: Study measures for PrEP-PP

Primary Outcomes	Measurement	Source	Frequency
PrEP initiation	# of women who initiate PrEP over time / total # of women in active cohort = proportion of women who initiate PrEP	Electronic provider log (REDCap)	Daily entry, weekly analysis

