PrEP retention	# of women on PrEP who return for study visits (do not miss more than 1 visit) / total # of women in active cohort who are prescribed PrEP= proportion of women on PrEP who are retained in PrEP study	Electronic provider log (REDCap)	Daily, analysis weekly
PrEP adherence-subjective	# of women taking PrEP, who self-report taking their medication daily (& pill count to confirm this) during periods of sexual risk over time / total woman-time on PrEP in active cohort = PrEP adherence rate (subjective)	Electronic provider log (REDCap)	Daily, analysis weekly
PrEP adherence-objective	# of women taking PrEP who have >80% levels at >40ng/mL TDF-DP (indicating dosing in past 24 hours) at 3 rd trimester, delivery, and 6 weeks postpartum (and during sexual risk periods during that time) / total woman-time on PrEP in active cohort = PrEP adherence rate (objective)	Lab analysis of TDF-DP measures	Quarterly
Secondary Outcomes			
Predictors of attrition at key steps in the PrEP cascade	Individual, pill/study and disease specific predictors of attrition	ACASI	ACASI: Every study visit
HIV outcomes	HIV testing data: HIV-uninfected, HIV-positive for mother and child (if mother seroconverts)	Electronic provider log (REDCap)	Every visit
Health outcomes and adverse events	Any side-effects, creatinine, any negative maternal or neonatal outcomes (for mother and infant)	Electronic provider log (REDCap)	During routine lab tests and visits

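### The primary objective-adherence outcome has two TDF-DP cut-offs, 100-fold apart if they share a matrix, and both adherence rows of Table 2 divide women by woman-time

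*Combined protocol and SAP*

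**What the plan says.** Section 5, laboratory tests in women on PrEP, DBS bullet: "adherence will be defined as red blood cells containing TDF-DP ≥ 40 ng/dl which is indicative of daily dosing". The same bullet adds: "We will determine final dosing and measures following reporting from ongoing PK studies of pregnant women on PrEP".

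Table 2 in section 6 lists objective adherence among the primary outcomes. Its numerator is women "who have >80% levels at >40ng/mL TDF-DP (indicating dosing in past 24 hours", at three named time points (third trimester, delivery and six weeks postpartum). The numerator's closing condition and the denominator read "and during sexual risk periods during that time) / total woman-time on PrEP in active cohort". The subjective-adherence row above it likewise puts a count of women over woman-time on PrEP.

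Section 6, statistical analysis considerations, makes the blood measure the main one: "Primary adherence analyses will use objective measures (TDF-DP from DBS) taken on all those who enrolled and initiated PrEP". It gives no cut-off there. For prevention-effective continuation it also plans "to create a semi-ordinal composite adherence score from blood specimens from DBS every 2-months", without stating the bands of that score.

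Objective 1(3) in section 2 asks for a proportion of women who initiate PrEP.

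**The concern.** A primary outcome should classify each woman in one way, whoever runs the analysis. Here one analyst could follow section 5 and another Table 2, and they could label the same sample oppositely.

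The label feeds the adherence step of the cascade, the mixed-effects probit and GEE models of adherence, and the comparison of self-report with the blood measure that is meant to show under- or over-reporting. Section 6 describes the study as a pilot whose product is estimates of the cascade, so the definition of the estimate matters even though no hypothesis test depends on it.

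The denominator raises a second difficulty. A number of women over an amount of time is not a proportion, and it moves with the length of PrEP use even when adherence does not change.

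**Working it through.** **Inputs**
- Cut-off A: at least 40 ng/dl, red blood cells, read as daily dosing (section 5, DBS bullet).
- Cut-off B: above 40 ng/mL, no matrix in the row, read as a dose within the last day (Table 2).
- Specimen: DBS, named in objective 1(3), the DBS bullet, the DBS row of Table 1 and section 6.
- Mean follow-up: 18 months (section 4).

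**Step 1: common unit.** 1 dl = 100 mL.
- A = 40 / 100 = 0.4 ng/mL.
- B = 40 ng/mL, or 40 × 100 = 4,000 ng/dl.
- B / A = 40 / 0.4 = 100, assuming one matrix.

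**Step 2: classification of one sample, same matrix assumed**

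| TDF-DP (ng/mL) | Under A | Under B |
|---|---|---|
| below 0.4 | not adherent | not adherent |
| 0.4 to 40 inclusive | adherent | not adherent |
| above 40 | adherent | adherent |

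If the two units were made the same, only a sample lying exactly on the cut-off would still be classified differently (at least versus above). The share of samples in the middle row cannot be computed, because the documents give no distribution of TDF-DP.

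**Step 3: the Table 2 ratio.** Let N women have a mean of T years on PrEP each, and let a proportion p of them meet the criterion.
- Ratio = pN / (NT) = p / T.
- With full adherence, p = 1 and the ratio is 1/T.
- Illustration: T = 1.5 years, which assumes unbroken PrEP use over the mean follow-up, gives 1 / 1.5 = 0.67 per woman-year.
- With an assumed T = 1 year and p = 2/3, the ratio is 0.67 / 1 = 0.67 per woman-year.

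Full adherence over 18 months and two-thirds adherence over 12 months therefore give the same value. The ratio cannot be read as a proportion, and for fixed p it rises as T falls.

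**Step 4: the base of >80%.** The row does not say what this is a percentage of. If the base is its own three time points, 2 of 3 is 66.7% and fails, so 3 of 3 is required.

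**The case against.** **The unit mismatch is an obvious slip.** Probably so, given the shared 40. But nothing in the documents shows which unit is the slip, and correcting it would leave the inequality and the two stated meanings unreconciled. Those meanings are not plainly incompatible, since a woman who doses daily has normally dosed in the last day. They still describe different things, a pattern and one recent dose. What the threshold really indicates rests on a cited source outside these documents.

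**The measure is provisional.** Section 5 defers final measures to external PK studies, and a cut-off can be applied later to recorded concentrations without loss of data. That keeps the repair cheap. But the deferral gives no rule for choosing and does not acknowledge the two values, so it does not resolve them.

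**The matrix is known.** This largely stands: DBS is named in four places, so the silence of the Table 2 row is a small matter. It also makes the 100-fold comparison more apt, although the red-cell wording in section 5 still needs squaring with DBS.

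**A rate is intended.** Section 6 does plan incidence densities alongside cumulative incidences, and Table 2 calls its ratios rates. That does not cure the ratio, because the numerator counts women who satisfy a criterion, not events or adherent time.

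**Assay timing.** A reader might infer that the documents contradict each other on when assays are run, and that results could be seen before the cut-off is set. Section 5 has cards "stored at -80°C for analysis at the end of the study", and the Table 2 row, with source "Lab analysis of TDF-DP measures", is marked *Quarterly*. But that word sits in a frequency column. Other rows use the column for collection, and where the table means analysis frequency it says so. *Quarterly* may therefore mean collection, and a conflict is not shown.

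**Conclusion.** The definition of the primary objective-adherence outcome is wrong as written and needs correcting before analysis. Its two cut-offs are 0.4 and 40 ng/mL. The 100-fold gap assumes a shared matrix, which the repeated naming of DBS supports but the red-cell wording leaves open. The documents do not support a claim about how far the adherence estimate would move, nor about which unit was meant.

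The count-over-time form in both adherence rows is a separate fault. It follows from algebra alone (p/T) and needs no assumption about the data; only the numerical illustration assumes durations.

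The base of >80% and the meaning of *Quarterly* are minor clarifications. A reader might take all scheduled Table 1 draws as the base of >80%. The row names its own three time points, so that reading is weak.

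**What to change.** - **Cut-off.** Reconcile the DBS bullet in section 5 and the Table 2 row to a single definition giving matrix, unit, inequality and meaning. Take it from the assay laboratory's validated method, use it identically in both places, and date the amendment before any DBS result is examined. If PK reports are to inform the choice, say so and say how.
- **Ratio.** Change both the subjective and the objective row, so that the two measures stay on one scale for the planned comparison. Either use women meeting the criterion over women who initiated PrEP and have evaluable data, reporting how many initiators lack such data, or use adherent woman-time over total woman-time on PrEP, with a rule for turning samples or reports into time. The first answers objective 1(3) directly.
- **Minor clarifications.** State the base of >80%. State whether *Quarterly* means collection or assay, given the plan to analyse stored cards when the study ends.

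The cost is a short amendment to one paragraph and two table rows, with no additional samples or assays.
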